### **3.2. Scientific Rationale for Study Design**

[figure not shown]
Based on the hypothesis that micro-dystrophin expression can improve sarcolemmal integrity resulting in improved cardiac and skeletal muscle function as well as preliminary results from the ongoing study (Study SRP-9001-101), this study will further assess the safety and efficacy of exogenous gene transfer in DMD patients measuring biologic and clinical efficacy endpoints.

### **3.3. CCI**

CCI

CCI

### **3.4. End of Study Definition**

The end of the study is defined as the date of last patient, last visit. Patients will have the opportunity to complete their 5-year post-infusion follow-up in a long-term extension study. The long-term extension study has been designed to provide a uniform approach to monitoring long-term safety and efficacy in subjects who received an infusion of SRP-9001 in a clinical trial.

Patients must complete the Week 130 visit at a minimum before rolling over into the long-term extension study. After completion of the Week 130 visit, if subjects decide not to continue their follow-up in the long-term extension study, subjects will complete an end of study visit.

## 4. STUDY POPULATION

Prospective approval of protocol deviations to recruitment and enrollment criteria, also known as protocol waivers or exemptions, are not permitted.

### 4.1. Inclusion Criteria

Participants are eligible to be included in the study only if all of the following criteria apply:

1. Male, 4 to 7 years of age, inclusive, at the time of screening in Part 1.
2. Molecular characterization of the DMD gene with either frameshift (deletion or duplication) between exons 18 to 58, or premature stop codon mutation between exons 18 to 58.
3. Indication of symptomatic muscular dystrophy:  
[REDACTED]  
[REDACTED]
4. Ability to cooperate with motor assessment testing.
5. Stable dose equivalent of oral corticosteroids for at least 12 weeks before screening and the dose is expected to remain constant (except for potential modifications to accommodate changes in weight) throughout Part 1 and 2 of the study.

[figure not shown]
### 4.2. Exclusion Criteria

Participants are excluded from the study if any of the following criteria apply:

1. Signs of cardiomyopathy, including ECHO [REDACTED]
2. Serological evidence of HIV infection, or Hepatitis B or C infection.
3. Diagnosis of (or ongoing treatment for) an autoimmune disease.
4. Concomitant illness or requirement for chronic drug treatment that in the opinion of the PI creates unnecessary risks for gene transfer.
5. Has a medical condition or extenuating circumstance that, in the opinion of the Investigator, might compromise the patient's ability to comply with the protocol required testing or procedures or compromise the patient's wellbeing, safety, or clinical interpretability.
6. Severe infection (eg, pneumonia, pyelonephritis, or meningitis) within [REDACTED] before study treatment infusion.
7. Demonstrates cognitive impairment that could confound motor development in the opinion of the Investigator.
8. Has received any investigational medication (other than corticosteroids) or exon skipping medications (including EXONDYS 51®), experimental or otherwise, within 6 months of screening.
9. Has received any type of gene therapy, cell-based therapy (eg, stem cell transplantation), or CRISPR/Cas9 therapy.

10. Abnormal laboratory values considered clinically significant:

CCI

A large black rectangular redaction box covers several lines of text. In the top-left corner of this box, the letters 'CCI' are printed in red.

11. Patients with rAAVrh74 antibody titers > 1:400 as determined by enzyme-linked immunosorbent assay (ELISA).
12. Family does not want to disclose patient's study participation with primary care physician and other medical providers.

#### **4.3. Lifestyle Considerations**

CCI Every effort should be made to collect these samples on the first day of a 2-day study visit; however, per PI discretion, the samples may be collected during a 1-day study visit. CCI samples must be collected before any functional assessments are performed. Parents or caregivers should be asked to limit patient's physical activity level over the 3 days before a visit where CCI samples will be collected.

#### **4.4. Screen Failures**

Screen failures are defined as participants who consent to participate in the clinical study but are not subsequently randomly assigned to study intervention.

Individuals who do not meet the eligibility criteria may be rescreened at the Investigator's discretion.

## 5. STUDY INTERVENTION

Study intervention is defined as any investigational intervention(s), glucocorticoid(s), or placebo intended to be administered to a study participant according to the study protocol.

### 5.1. Study Intervention(s) Administered

	Micro-dystrophin	Placebo	Corticosteroid
Intervention Name	SRP-9001 gene vector	Lactated Ringer's solution	Glucocorticoid
Type	Vector	Placebo	Immunosuppressant
Dose Formulation	IV infusion	IV infusion	Oral or IV
Dose a	$1.33 \times 10^{14}$ vg/kg	NA	1 mg/kg (prednisone equivalent)
Dosage Level(s)	Single dose	Single dose	Day before infusion and continuing for at least 60 days after the infusion unless earlier tapering is judged by the Principal Investigator to be in the best interest of the patient
Route of Administration	IV infusion (peripheral limb vein)	IV infusion (peripheral limb vein)	Oral or IV

IV = intravenous; NA = not applicable; qPCR = quantitative polymerase chain reaction.

aFor patients who received a dose in this study based on Nationwide Children's Hospital qPCR method, the dose used was  $2 \times 10^{14}$  vg/kg which corresponds to  $1.33 \times 10^{14}$  vg/kg as measured by the Sponsor's qPCR method using a linear standard.

#### 5.1.1. Pre-infusion Immunosuppressants

The day before the infusion, the patient's background dose for DMD will be increased to at least 1 mg/kg of a glucocorticoid (prednisone equivalent).

#### 5.1.2. Post-infusion Immunosuppressants

Patients will remain on their stable dose of corticosteroids throughout Part 1 and 2 of the study but will be increased to at least 1 mg/kg of a glucocorticoid (prednisone equivalent) for at least 60 days after the infusion unless earlier tapering is judged by the PI to be in the best interest of the patient. Additional glucocorticoid may be utilized if GGT level is > 150 U/L or there are other clinically significant liver function abnormalities following infusion. A tapering dose of glucocorticoid will be implemented based on individual patients' immune response to the infusion, assessed by liver function monitoring with GGT. This monitoring will be done by the Treating Team who will also monitor AEs. If there are signs of immune response in specific

organ systems like the liver, the Treating Team will closely monitor and make adjustments in glucocorticoid dosing.

### **5.1.3. Intravenous Infusion (Day 1, Part 1 and Part 2)**

SRP-9001 or placebo administration will be through a peripheral limb vein. Administration will be performed according to the Site-Specific Pharmacy and/or Dose Administration Manual.

### **5.1.4. Post Infusion Monitoring**

#### **5.1.4.1. Immediately Following Infusion**

Vital signs will be monitored during and after the infusion according to the Study Operations Manual. Concomitant medications and all AEs and SAEs will also be monitored and documented following injection.

#### **5.1.4.2. Extended Follow-up**

Patients will return for clinic follow-up visits as outlined in the Schedule of Activities. Patients must complete the Week 130 visit at minimum before rolling over into the long-term extension study. After completion of the Week 130 visit, if patients decide not to continue their follow-up in the long-term extension study, patients will complete an end of study visit.

CCI

Unscheduled visits and additional blood draws may occur if the Investigator determines they are necessary for the patients' safety and wellbeing.

## **5.2. Preparation/Handling/Storage/Accountability**

Compliance standards for Biosafety Level 1 vectors must be followed according to standard pharmacy protocol for handling investigational products similar to SRP-9001.

## **5.3. Measures to Minimize Bias: Randomization and Blinding**

### **5.3.1. Establish Patient Identification Number**

All patients will be given a unique sequentially assigned patient identifier. Patients will be identified only by this number in order to protect identity.

### **5.3.2. Assignment to a Treatment Group**

This is a double-blind study. Patients who have signed the informed consent and who meet all eligibility will be randomized using the IXRS to 1 of the 2 treatment groups prior to or on Day -1 in Part 1.

### 5.3.3. Randomization

Patients will be randomized in a 1:1 ratio by the IXRS in Part 1 of the study to receive either SRP-9001 or placebo. Patients randomized to SRP-9001 in Part 1 of the study will receive placebo in Part 2. Patients randomized to placebo in Part 1 of the study will have the opportunity to receive SRP-9001 in Part 2.

Randomization will be stratified by age group at Baseline (4-5 vs 6-7 years). To ensure approximately equal numbers of patients are assigned to the 2 treatment groups (SRP-9001 vs placebo) in Part 1, each age group must have a multiple of 4 patients.

### 5.3.4. Blinding/Unblinding

All patients and study staff will be blinded to treatment assignments with the exception of the pharmacist until the last patient completes the [\[cc1\]](#) visit. The blind of the treatment may be broken only in exceptional circumstances, such as when knowledge of the study treatment is essential for treating a patient due to an SAE. If time permits, the Investigator must contact the unblinded CRO Medical Director before unblinding of the patient. If time does not permit, the Investigator may authorize breaking of the blind and then notify the unblinded CRO Medical Director. The study treatment information should be disclosed only to personnel who need the information for the medical care of the patient. If the study treatment is unblinded, the patient number, time, date, and reason for unblinding must be recorded in the study records. Study personnel who were unblinded should be identified. Refer to the study unblinding plan for further details regarding the unblinding of the study for Part 3.

Separate study personnel will be designated to conduct functional assessments and to treat patients in order to protect against possible unblinding of treatment assignment during regular clinical care of patients.

The PI will designate the following investigational site personnel:

- An Examining Team
- A Treating Team

The Examining Team will be:

- Composed of physiotherapists trained in the proper execution of the physical functional assessments (NSAA, 10-meter timed test, 100-meter timed test, time to rise from floor, and time to ascend 4 steps)

The Treating Team will be:

- Composed of clinicians who will be responsible for the following:
  - Administering the study treatment
  - Conducting the patient's follow-up visits but not the physical functional assessments at those visits per the SoA (Section [1.3](#))
  - Review of all clinical and safety laboratory results
  - Glucocorticoid dose adjustments
  - Assessment of AEs, SAEs, and TEAEs
  - Management of the routine care of the patient

The physiotherapists from the Examining Team will be responsible for conducting the physical functional assessments (NSAA, 10-meter timed test, 100-meter timed test, time to rise from floor, and time to ascend 4 steps). They will not have access to any patient data and must be restricted from having access to AEs, concomitant medications, laboratory data, and any other data that have the potential of revealing the treatment assignment. The physiotherapists should be instructed not to have conversations with the patients and parents/caregivers about their progress in the study.

The Treating Team members will be responsible for the clinical care of the patient. They will manage the study drug infusion, steroid dosing changes, review all laboratory data, assess AEs and SAEs, and perform all assessments except for the physical functional assessments (NSAA, 10-meter timed test, 100-meter timed test, time to rise from floor, and time to ascend 4 steps). The Treating Team will not have access to the data collected by the Examining Team.

The study will be unblinded once the last patient completes the **cci** visit; refer to the study unblinding plan for further details.

#### **5.4. Concomitant Therapy**

To be collected from the time of consent until final study visit, recorded on the case report form (CRF).

Any medication or vaccine (including over the counter or prescription medicines, vitamins, and/or herbal supplements) that the participant is receiving at the time of enrollment or receives during the study must be recorded in the CRF.

If a reaction to the infusion occurs, the Treating Team should treat the reaction. The date and time of medication administration as well as the name and dosage regimen must be recorded.

##### **5.4.1. Rescue Medicine**

There are no specific rescue medications for use in this study that will turn off SRP-9001 transgene expression. Corticosteroid therapy, at the PI's discretion, may be used to manage possible liver-associated adverse effects of SRP-9001.

#### **5.5. Dose Modification**

##### **5.5.1. Stopping Rules**

Study enrollment will be interrupted when any patient experiences 1 or more Grade 3 (severe) or higher AEs that are unexpected as related to gene therapy or DMD. This will include any patient death, important clinical laboratory findings, or any severe local complication in the injected area related to administration of the study agent. The findings will be reported to the data monitoring committee (DMC). If after review by the DMC, the recommendation is made to continue, the Sponsor may decide that the study will proceed.

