##### **3.1.2. Treatment Period**

###### **3.1.2.1. Part 1**

Part 1 is a 48-week randomized, double-blind, placebo-controlled period. Patients meeting eligibility requirements will be randomized prior to or on Day -1 to SRP-9001 or placebo in a 1:1 ratio by IXRS. Up to 22 patients will receive IV SRP-9001 ( $1.33 \times 10^{14}$  vg/kg) and up to

22 patients will receive a matching volume (up to 10 mL/kg) of placebo (lactated Ringer's solution).

Patients may be admitted to the hospital the day before the study treatment is infused at the discretion of the Investigator. On Day -1, the patient will receive a physical examination, have vital signs collected, and provide blood and urine samples.

The day prior to the study treatment infusion (SRP-9001 or placebo), patient's background dose of steroid for DMD will be increased to at least 1 mg/kg of a glucocorticoid (prednisone equivalent) daily and continue at this level for at least 60 days after the infusion unless earlier tapering is judged by the PI to be in the best interest of the patient.

SRP-9001 or placebo will be administered IV on Day 1 over 1 to 2 hours. Vital signs will be monitored during and after the infusion according to the Study Operations Manual.

On the day after the infusion (Day 2), patients will receive a physical examination, have vital signs collected, and provide blood and urine samples before being discharged or in clinic, as applicable.

Patients will be followed for 48 weeks in Part 1. Patients will complete clinic follow-up visits at the following time points: **cci** relative to the infusion on Day 1). In addition, at **cci**, patients will complete follow-up visits for assessment of liver function tests. If the **cci** visits occur in the clinic, a blood sample for the assessment of glutamate dehydrogenase (GLDH) will be collected.

All patients will have a muscle biopsy performed at Week 12 in Part 1. **cci**

All patients, parents, caregivers, the Examining Team, the Treating Team, physiotherapists, and clinical staff will be blinded to the treatment the patient receives (SRP-9001 or placebo). The study will be unblinded when the last patient completes the **cci** visit. Refer to the study unblinding plan for additional details.

Safety will be assessed by monitoring of treatment-emergent adverse events (TEAEs), serious adverse events (SAEs), and select laboratory assessments.

Refer to Section 6 Study Assessments and Procedures for additional information.

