##### **5.5.2. Dosing Schedule**

Based on the safety profile of systemic gene delivery clinical trial (Study SRP-9001-101) for DMD using SRP-9001, there will be at least a 1-week interval between dosing each patient for the first 4 patients.

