### 6.3. Adverse Events and Serious Adverse Events

#### 6.3.1. Collection of Adverse Events

Over the entire duration of the study, site personnel will ensure that all AEs are recorded appropriately. If an AE occurs, the primary concern is for patient safety, and the Investigator will use his/her judgment and expertise to determine the appropriate course of action.

All AEs from the time of informed consent through the last follow-up visit will be recorded in each enrolled patient's CRF. For consented patients who are found to be ineligible for the study during the Screening period and are not enrolled (ie, Screening failures), only SAEs will be collected.

If, at any time after the patient has completed participation in the study, the Investigator or study staff becomes aware of an SAE that the Investigator believes is possibly/probably or definitely related to the investigational product (IP) or is possibly/probably or definitely related to a study procedure, then the event and any known details must be reported promptly to the Sponsor.

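### The stopping rule requires an enrollment interruption and a report to the DMC, but its visible wording does not require holding infusions for patients already enrolled

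*Combined protocol and SAP*

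**What the plan says.** Protocol Section 5.5.1 is readable in full. Its trigger is a single unexpected event, and deaths are expressly included: "Study enrollment will be interrupted when any patient experiences 1 or more Grade 3 (severe) or higher AEs". The findings must then go to the DMC. If the DMC recommends continuing, "the Sponsor may decide that the study will proceed". Dosing, infusions and Part 2 are not mentioned.

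Section 5.5.2, directly below, restricts dosing in so many words, but only at the start of the trial: "there will be at least a 1-week interval between dosing each patient for the first 4 patients".

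Section 3.1.2.1 fixes when a patient enters: "Patients meeting eligibility requirements will be randomized prior to or on Day -1 to SRP-9001 or placebo in a 1:1 ratio by IXRS". It also caps the control group: up to "22 patients will receive a matching volume (up to 10 mL/kg) of placebo". Under Section 3.1.2.2 each patient starts Part 2 after completing his 48-week Part 1. Those first given placebo are then due SRP-9001, and those first given SRP-9001 are due placebo, which preserves the blind.

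**The concern.** In a trial with one infusion per patient soon after entry, pausing entry stops nearly all new exposure. This trial crosses over: up to half of the SRP-9001 infusions are planned for patients who entered roughly a year earlier. A rule that acts on enrollment does not reach them.

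The order of events matters because the treatment cannot be reversed. Section 5.4.1 says that no rescue medication will switch off transgene expression, so a pause protects a patient only if it comes before his infusion. If a qualifying event, even a death, occurs after the last randomization, the event goes to the DMC. Whether pending Part 2 infusions wait for that review is then left, in the visible text, to someone's discretion. Meanwhile the sites' written default is to dose: Section 3.1.2.2 directs the Part 2 infusion, and Section 9.1.1 allows departures from the protocol only in emergencies.

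**Working it through.** **Step 1: what enrollment means.** The protocol gives no formal definition, so its usage has to be compared across sections.

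- Section 6.3.1 treats patients who "are not enrolled (ie, Screening failures), only SAEs will be collected". Not being enrolled is thus the same as failing screening.
- Section 4.4 defines screen failures as those who consent "but are not subsequently randomly assigned to study intervention".
- Taken together, a patient who has been randomized is enrolled. By Section 3.1.2.1 that happens on or before Day -1 of Part 1.
- Section 5.4 separates two times for medication use, what "the participant is receiving at the time of enrollment or receives during the study". Enrollment is a point of entry, distinct from the period that follows.
- Sections 4 and 6.2.4 also use the word for eligibility and entry.
- Section 5.5.2 says dosing when it means dosing.

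Interrupting enrollment, so read, stops new patients from entering. It does not reach a patient already randomized, whether he awaits Day 1 of Part 1 or the Part 2 infusion.

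**Step 2: what else could require a hold.**

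| Section | Provision | Hold required when 5.5.1 is triggered? |
|---|---|---|
| 5.5.1 | Report to the DMC | Review is required, a hold is not |
| 5.6 | Halt for unexpected risk, after consultation | No, permitted |
| 6 | Prompt discussion with the Sponsor about the participant | No, case by case |
| 7.6 and 9.2.1 | Periodic DMC review, advisory | No, recommendation only |
| 3.1.2.2 | Part 1 placebo patients with titers above 1:400 are not dosed | No, another patient's event does not trigger it |

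**Step 3: how many infusions.** Inputs: at most 44 patients (Section 3.1) and 1:1 allocation (Section 5.3.3).

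- Part 1 placebo patients: 44 × 1/2 = 22, which reproduces the protocol's own ceiling.
- SRP-9001 infusions over both parts: 22 + 22 = 44 at most. Share in Part 2: 22/44 = 50%.
- Part 2 infusions of either kind, which the proposed hold would cover: 22 SRP-9001 + 22 placebo = 44 at most.

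The number of SRP-9001 infusions pending at an event runs from 22, if all placebo patients have entered and none has crossed over, down to 0. Titers above 1:400, withdrawals and completed crossovers reduce it.

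**Step 4: how long.** The last patient is randomized by Day -1, and his Part 2 infusion follows his 48-week Part 1. The interval with no enrollment left to interrupt and a Part 2 infusion still due is therefore about 48 weeks; visit windows are not visible. If this patient received SRP-9001 in Part 1, his Part 2 infusion is placebo, and the last SRP-9001 infusion may fall earlier.

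These are counts and durations. The documents give no rate for the triggering event, so no probability can be attached.

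**The case against.** The strongest reply is that 5.5.1 already means a study-wide pause. It is headed as a stopping rule, stands under dose modification, and ends with the Sponsor deciding whether the study goes on, which makes sense only if the study has paused. The meaning of enrollment is also pieced together from sections on other subjects. This stands as evidence of intent. It does not supply an instruction to hold an infusion, and if a full pause is intended, the rewording merely says so.

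A reader might infer that nobody could stop Part 2 dosing, or that dosing would go on after a death. The documents do not support that. Section 5.6 lets the Sponsor, the investigator, the DMC, ethics committees or regulators prompt a halt, and lists unexpected risk among the grounds. Section 6 calls for immediate discussion of safety concerns, and Section 6.3.3.8 sends unexpected serious reactions unblinded to regulators. What is absent from the readable text is a required hold, not the power to impose one.

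Nor is the rule empty once enrollment closes, because the DMC report is still mandatory.

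Redaction also limits the point. Part of the Part 2 text in Section 3.1.2.2, just before the antibody check, is blacked out, as is the Schedule of Activities, and the DMC charter is not supplied. A dosing hold may be stated there, so it cannot be said that the plan lacks one.

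Finally, a hold has a price: one event in any patient could delay the placebo patients' access to SRP-9001 within the study.

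**Conclusion.** The point holds for Section 5.5.1 as visibly worded: two actions are mandatory, and neither holds an infusion for a patient already enrolled. At most 22 Part 2 SRP-9001 infusions are affected, plus any randomized patient awaiting Day 1.

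It would be too strong to say that SRP-9001 infusions go unprotected for 48 weeks. That figure runs to the last patient's Part 2 infusion of either kind, and the discretionary routes remain open throughout.

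The conclusion assumes that enrollment means study entry and that no hidden or separate text already requires a hold. It is best treated as a cheap improvement: discretionary safeguards exist, but a pause before an irreversible dose should not rest on them alone.

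**What to change.** Reword Section 5.5.1 so that the same trigger interrupts enrollment and all pending study infusions in Parts 1 and 2, until the DMC has reviewed the event and the Sponsor has decided. Hold SRP-9001 and placebo infusions alike, since holding only one would reveal the assignments. If the redacted Part 2 text or the DMC charter already contains such a hold, a cross-reference in 5.5.1 is enough.

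The cost is protocol wording and possible short delays to Part 1 or Part 2 dosing while the DMC reviews, including to placebo patients' access to SRP-9001. Sample size and analysis are not changed.
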